### **2.1.2.3 ANTIBIOTIC PRESCRIPTIONS**

There are three outcomes related to antibiotic prescriptions for pre-defined infections throughout the trial. Information regarding antibiotics will be obtained from the 12 months notes review, the SystmOne reports, and the post antibiotic telephone call. The outcomes of interest are:

- 1) Antibiotic usage in terms of number of prescriptions,
- 2) Number of days of treatment,
- 3) Defined daily dose (DDD),

Each outcome will be calculated separately for all antibiotics of interest, and split by antibiotic type (penicillin, and non-penicillin) as well as antibiotic class (see spreadsheet: K:\ID\ALABAMA\STATS\2. Stats Plan and Sample Size\SAP\ABX categories & DDD for analysis\_07Aug2023.xlsx). A list of the pre-defined infections of interest can be found in Appendix G of the protocol, and Appendix II of this document. Long term antibiotic prescriptions, defined as periods of continuous use for  $\geq 3$  months used for prophylaxis or “anti-inflammatory” indications will be excluded from the analyses.

#### **2.1.2.3.1 NUMBER OF ANTIBIOTIC PRESCRIPTIONS**

This outcome will be derived from the notes review question “*Please list all the antibiotics the patient was treated with for the above event or symptoms*” (Variable *ABXNAME*), as well as data from the SystmOne report and hospital prescribing report (if available). This outcome will be derived as the number of antibiotic prescriptions up to 12 months post-randomisation. If there is no evidence of antibiotic usage this outcome will be coded as zero. A “prescription” will be considered to be an uninterrupted period of antibiotic use. Where a period of at least 2 days separates prescriptions for the same antibiotic, these will be considered separate prescriptions.

If the patient had a relevant infection event but there is no prescription data for that patient then this outcome will be missing. Patients who also withdrew before 12 months who do not have an antibiotic prescription, and who withdrew consent for notes reviews to be conducted will also have this outcome missing.

#### **2.1.2.3.2 NUMBER OF DAYS OF TREATMENT**

This outcome will be derived from the start and stop dates across the different data sources: the SystmOne report and the notes review (Variables *ABXPRESTARTDAT*, *ABXPRESTOPDAT*) and hospital prescribing report. The total number of days the participant was taking antibiotics for each prescription event will be added to give the total days prescribed antibiotic treatment for the 12-month period. This will be calculated as the stop date minus the start date plus one, if there is no evidence of antibiotic usage this outcome will be zero. If a patient has the antibiotic usage outcome (above) missing, then this outcome will also be missing.

#### **2.1.2.3.3 DEFINED DAILY DOSE (DDD)**

This outcome will be derived from the notes review question “Dose” (Variable *ABXDOSE*) and “Units” (Variable *ABXUNITS*), as well as the SystmOne report and hospital prescribing report. The doses will need to be standardised into grams before DDD can be calculated. Each participants’ defined daily dose will be calculated using the formula (Total dose in grams \* Total treatment duration) / DDD factor, if there is no evidence of antibiotic usage this outcome will be zero. If a patient had the antibiotic usage outcome (above) missing, then this outcome will also be missing.

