### 5.2 CONTINUOUS OUTCOMES

The continuous secondary outcomes:

- Duration of symptoms rated ‘moderately bad’ or worse,
- Number of days of antibiotic use (total and split by penicillin and non-penicillin, and antibiotic class)
- Defined daily dose (DDD) (total and split by penicillin and non-penicillin and antibiotic class),
- And length of hospital stays,

will be analysed using a linear mixed effects regression model. The models will include randomised group, age, number of antibiotic prescriptions in the 24 months prior to randomisation (12 months for those recruited to the nested pilot study), and the number of QOF registered diseases as fixed effects. GP practice will be included as a random effect. The adjusted mean difference between the randomised groups with 95% confidence intervals and P-values will be reported.

The proposed analyses assumes that these secondary outcomes satisfy the assumptions of the linear mixed effects regression model. Histograms of the distribution of each outcome split by randomised group, and post estimate plots of the residuals will be presented. If the post estimate plots show evidence that the assumptions of the linear mixed effects regression model have been violated, transformation of the data will be attempted. If there is still evidence that the assumptions have been violated a quantile regression will be implemented. The quantile regression will include randomised group, age, number of antibiotic prescriptions in the 24 months prior to randomisation (12 months for those recruited to the nested pilot study), number of QOF registered diseases, and GP practice as covariates. The adjusted median difference between the randomised groups with

95% confidence intervals, and P-values will be reported. If the quantile regression does not converge an unadjusted quantile regression will be attempted; if the model still does not converge a non-parametric approach such as a Mann-Whitney U test will be adopted.

Defined daily dose (DDD) split by class, is expected to be small for some classes in each randomised arm. If it is judged to be too small this will only be presented descriptively.

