## **11 VALIDATION**

At a minimum the primary analysis, and safety analysis in the statistical analysis report will be validated. Validation will be conducted by a senior trial statistician or delegate, and will not be the same person who performed the main analysis, or authored the SAP.

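### The DDD formula multiplies a total dose by duration, so duration counts twice, and it omits the per-prescription, drug-specific sum that the outcome needs

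*SAP*

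**What the plan says.** Section 2.1.2.3.3 defines the outcome at participant level: the "defined daily dose will be calculated using the formula (Total dose in grams" multiplied by "Total treatment duration) / DDD factor". On units it says only "The doses will need to be standardised into grams before DDD can be calculated". It does not describe the dose as daily, apply the formula to each prescription, give each drug its own factor, or say that results are added up.

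Three other places bear on this:

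- Section 2.1.2.3, the parent section, says "Each outcome will be calculated separately for all antibiotics of interest, and split by antibiotic type" and also by class. It cites a spreadsheet whose file name refers to antibiotic categories and DDD.
- Section 2.1.2.3.2 adds treatment days over prescription events to give a 12-month total. Section 2.1.2.3.3 has no equivalent sentence for DDD.
- Section 5.2 lists "Defined daily dose (DDD) (total and split by penicillin and non-penicillin and antibiotic class" among the continuous outcomes, to be compared between arms with a confidence interval and P-value.

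**The concern.** There are two separate problems.

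First, a DDD factor is an amount per day. Dividing total grams by it yields the number of DDDs, and nothing more is needed. The written formula then multiplies by duration. The resulting error equals the number of days treated, so it is not a constant scale factor and need not cancel between arms.

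Second, the formula uses one total dose, one total duration and one factor per participant. A total over all antibiotics mixes drugs with different factors, and a class can also hold several drugs. Without a per-prescription calculation, doses of one drug are multiplied by the days of another and divided by a factor that belongs to only one of them. The intervention is meant to shift prescribing between penicillins and alternatives, so the drug mix may differ by arm and this error cannot be assumed neutral.

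DDD is one of three measures for the secondary objective on total antibiotic prescribing. Section 11 promises only that "At a minimum the primary analysis, and safety analysis in the statistical analysis report will be validated", so an independent check of this derivation is not assured.

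**Working it through.** The SAP states no DDD figure to reproduce. The check is therefore one of units, followed by worked examples. **All doses, durations and factors below are assumptions chosen for arithmetic only.**

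**Units.** A DDD factor is in grams per day.

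- Course grams ÷ factor: g ÷ (g/day) = days, that is, a number of DDDs.
- Formula as written, with total dose as course grams: (g × days) ÷ (g/day) = days². Duration enters twice.
- Formula with a daily dose in its place: (g/day × days) ÷ (g/day) = days. This is correct for one course of one drug.

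**One course, factor 1.5 g**

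| Course | Course grams | Grams ÷ factor (correct) | As written | Daily-dose reading |
|---|---|---|---|---|
| 1.5 g/day, 5 days | 7.5 | 7.5 ÷ 1.5 = 5 | 7.5 × 5 ÷ 1.5 = 25 | 1.5 × 5 ÷ 1.5 = 5 |
| 1.5 g/day, 7 days | 10.5 | 10.5 ÷ 1.5 = 7 | 10.5 × 7 ÷ 1.5 = 49 | 1.5 × 7 ÷ 1.5 = 7 |
| 0.75 g/day, 10 days | 7.5 | 7.5 ÷ 1.5 = 5 | 7.5 × 10 ÷ 1.5 = 50 | 0.75 × 10 ÷ 1.5 = 5 |

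The 7-day to 5-day ratio is 7 ÷ 5 = 1.4 when computed correctly and 49 ÷ 25 = 1.96 as written. Rows 1 and 3 have the same true use, 5 DDDs, but score 25 and 50.

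**Two courses of the same drug in one participant** (1.5 g/day for 5 days and for 7 days, factor 1.5 g)

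- Summed per prescription: 5 + 7 = 12.
- Participant totals, daily-dose reading: (1.5 + 1.5) × 12 ÷ 1.5 = 24.
- Participant totals, course grams: (7.5 + 10.5) × 12 ÷ 1.5 = 144.

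**Two different drugs in one participant** (A: 1.5 g/day, 5 days, factor 1.5 g; B: 0.2 g/day, 7 days, factor 0.1 g)

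- Summed per prescription with each drug's own factor: 5 + (0.2 × 7 ÷ 0.1) = 5 + 14 = 19.
- Participant totals, daily-dose reading: (1.5 + 0.2) × 12 = 20.4, then ÷ 1.5 = 13.6 or ÷ 0.1 = 204, depending on whose factor is used.
- Participant totals, course grams: (7.5 + 1.4) × 12 = 106.8, then ÷ 1.5 = 71.2 or ÷ 0.1 = 1068.

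The daily-dose reading thus repairs the single course but not a participant with more than one course or drug.

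**The case against.** The strongest reply is that this is loose labelling. Section 2.1.2.3.3 starts from recorded dose and units and then multiplies by duration, which makes sense if the recorded dose becomes a daily dose. From those items alone, an analyst would have to multiply by days to build a course total and then multiply by days again, which few would do. The parent section already cites a spreadsheet that probably holds drug-specific factors, and the section just before it sums over prescription events. Pooling different drugs under one factor would be a strained reading. Section 11 sets a minimum for validation, and section 1.2 separately expects quality control of the data.

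Part of this stands. The daily-dose meaning is likely, the actual code may be right, and the figures of 25, 49 and 50 arise only under the literal reading. How dose per day is extracted from the recorded items is derivation detail that may sit in documents not shown, and is not held against the plan.

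Two things do not go away. The stated rule, followed as written, gives wrong values. The daily-dose reading also leaves it wrong at participant level, where the formula is defined. A list of factors does not say how they are applied and combined, and a summing rule for days is not a summing rule for DDDs.

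**Conclusion.** The point holds. As written, the formula overstates a single course by a factor equal to its length in days. On the likely intended reading it is right for one course of one drug, but it still does not provide the per-prescription, drug-specific sum that the totals in sections 2.1.2.3 and 5.2 require.

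The numerical illustrations rest on assumed doses, durations and factors. The size and direction of any effect on the comparison between arms cannot be derived from the SAP. The problem is confined to one secondary outcome and its splits; the primary outcome, prescription counts, treatment days and sample size are unaffected. It should be corrected before analysis. Because section 1.2 requires deviations from the plan to be described and justified, correct code would otherwise have to be reported as a departure from the written formula.

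**What to change.** Replace the formula in section 2.1.2.3.3 with wording to this effect: for each prescription, DDDs = (daily dose in grams × days of that prescription) ÷ that antibiotic's own DDD factor, taken from the spreadsheet cited in section 2.1.2.3; or equivalently course grams ÷ factor, with no further multiplication by duration. Each participant's value is the sum over prescriptions, formed overall, by penicillin and non-penicillin, and by class. A short note on how daily dose is obtained from the recorded dose and units and the prescribing reports would help but is secondary.

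The cost is one or two sentences and a check of the derivation code. No new data source is needed, provided those already planned hold dosing frequency or quantity supplied.

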#### **2.1.2.4 HOSPITAL ADMISSIONS**

Information regarding hospital admissions will be obtained from the HES data, post antibiotic day 28-30 telephone call, and the notes review. This outcome will be derived as:

- i) A binary variable (yes/no) if there is any evidence that the participant had a hospital admission in the 56 days after the start of a primary event, during the 12 months post-randomisation,
- ii) The number of hospital admissions in the 56 days after the start of a primary event, during the 12 months post-randomisation. If there is no evidence of hospitalisation this outcome will be zero,
- iii) The total number of days of hospitalisation in the 56 days after the start of a primary event, during the 12 months post-randomisation. If there is no evidence of hospitalisation this outcome will be zero.

Outcomes above only apply to admissions in the 56 days after start of a primary event, an exploratory analysis will also be conducted for all admissions during the 12 months post-randomisation.

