### 1.4.2 SECONDARY OBJECTIVES

- 1) To determine whether the PAAP intervention is clinically effective in improving treatment response failure,
- 2) Effects of PAAP on symptom duration,
- 3) Effects of PAAP on total antibiotic prescribing,
- 4) Effects of PAAP on hospital admissions and length of hospital stays (safety outcomes),
- 5) Effects of PAAP on mortality rates (safety outcome),
- 6) Effects of PAAP on Meticillin-resistant *Staphylococcus aureus* (MRSA) infection/colonisation,
- 7) Effects of PAAP on *Clostridioides difficile* infection,

- 8) To explore patient and clinical views and experiences of penicillin allergy testing, test results, and future antibiotic use,
- 9) (Process evaluation) To explore patient and clinician experiences of trial procedures,
- 10) To measure the influences on clinician and patient behaviour change regarding prescribing and consuming penicillin following a negative test result,
- 11) Cost effectiveness for the PAAP intervention compared to usual care,
- 12) Effects of PAAP on de-labelling:
  - a) at 3 months post randomisation,
  - b) up to 12 months post randomisation.
- 13) Additional safety outcomes (exploratory outcome)
- 14) Effects of PAAP on all outcomes for follow up post 12 months.

N.B. Objectives 8, 9, 10, and 11 will be analysed as part of the qualitative, economic, and process evaluation and will be reported separately from the main statistical analysis report.

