Regular reports were run in the ALABAMA unit to identify participants who had been prescribed an antibiotic, for any cause, in the previous 7 days. A member of the research team sent an alert to the trial research nurses team who then followed the participant up for the duration of the associated infection. The research team then designated an antibiotic prescription as a ‘primary event’ if the patient was prescribed an antibiotic for a pre-defined list of infections (see Appendix II). Participants receiving antibiotics for a primary event, were asked to complete a symptom diary. At the end of the follow up period their electronic health records were reviewed to ensure we had captured all antibiotic events. All trial participants had case note review and, if required had capture hospital episode statistics, and mortality data.

Throughout this process general practice staff and participants received behaviour change intervention materials.

See Appendix III for study flowchart.

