### **2.1.1 PRIMARY OUTCOME – EFFECTS OF PAAP ON PENICILLIN PRESCRIBING**

The primary outcome is the effect of PAAP on penicillin prescribing, and is defined as: the proportion of participants who receive prescriptions for a penicillin when attending for predefined conditions where a penicillin is the first-line recommended antibiotic (see Appendix II) up to 12 months post-randomisation.

The primary outcome will be coded as 1 (“Yes”) if there is evidence of a penicillin prescription during the course of routine care, up to 12 months post randomisation on any of the following data sources: SystmOne report/notes review (Variable *ISPRIMARYEVENT*), patient follow-up calls, or hospital prescribing reports. Participants that have not required penicillin treatment during the trial will have their primary outcome coded as 0 (“No”).

Participants who do not have evidence of a prescription and who withdrew consent for notes review to be conducted, will have their primary outcome missing at 12 months.

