#### **2.1.2.5 MORTALITY RATES**

Information regarding mortality will be obtained from the 12-month combined notes review question “*Is the participant alive?*” (Variable *ISALIVE*), the SAE report (Variable *SAESER*), the HES database, the ONS database, and the SystmOne report. This outcome will be derived as a binary variable and will be coded as affirmative if there is evidence of death on any of the sources listed above, this outcome will be coded as negative if there is no evidence of death on any of these sources. If there is a contradiction between the sources the participant will be assumed to have died. If a participant had withdrawn consent to note review/follow-up and there is no evidence of a death prior to withdrawal, then this outcome will be missing.

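### Hospital admission outcomes, declared safety outcomes, are coded zero when nothing is recorded, with no exception for participants whose records were not observed

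*SAP*

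**What the plan says.** Secondary objective 4 in SAP section 1.4.2 labels hospital admissions and length of stay as safety outcomes. Section 2.1.2.4 names three sources: "Information regarding hospital admissions will be obtained from the HES data, post antibiotic day 28-30 telephone call, and the notes review". It then derives three outcomes, each limited to the 56 days after the start of a primary event:

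- a yes/no item, scored yes on any evidence of an admission in that window, with 'no' left as the implied alternative;
- the number of admissions, with the rule "If there is no evidence of hospitalisation this outcome will be zero";
- the total days in hospital, with the same rule repeated.

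The section has no rule for withdrawal or for unobserved records.

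Other outcomes in the same SAP do have one. In section 2.1.1, participants with no prescription evidence who withdrew consent for notes review "will have their primary outcome missing at 12 months". Sections 2.1.2.1 (response failure), 2.1.2.3.1 (prescriptions, carried into days of treatment and DDD) and 2.1.2.8 (3-month de-labelling) have similar rules. The mortality rule in section 2.1.2.5, from its condition onward, is: "participant had withdrawn consent to note review/follow-up and there is no evidence of a death prior to withdrawal, then this outcome will be missing".

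**The concern.** The SAP fixes the derivation itself, so this is not a detail left to the protocol. The default is that absence of evidence equals absence of admission, for everyone. Two safety outcomes that share HES as a source are treated in opposite ways when a participant withdraws.

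There is also an internal conflict. A primary event is an antibiotic prescription for a listed infection. For a participant who withdrew early with no recorded prescription and no consent for notes review, section 2.1.2.3.1 calls the number of such prescriptions missing. Section 2.1.2.4 nevertheless sets admissions following such a prescription to zero. The trigger is treated as unknown and its consequence as known.

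The filled-in zeros would enter the models in sections 5.1 to 5.3 as observed data, so the missing-at-random argument in section 4.2 never applies to them. The effect is to count unobserved participants as unharmed.

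**Working it through.** **Does anything elsewhere repair the rule?** Section 3.3 expects missing data from withdrawal but gives no coding rule. Section 4.2 works through missingness of the primary outcome only. Section 6 limits sensitivity analyses to the primary outcome. Section 2 says participants, "if required had capture hospital episode statistics, and mortality data", without saying whether linkage continues after withdrawal. Nothing fills the gap.

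**Inputs.** The SAP gives no admission rate and no rate of withdrawal from notes review. Its nearest figure is the 10% attrition in section 2.3. Applied to the planned 848, that is 0.10 × 848 = 84.8, or about 85 participants. This is a loose ceiling, because general attrition is wider than withdrawal of consent for notes review. The following are assumptions: a 5% control admission risk, withdrawal of 5% to 15%, and withdrawal unrelated to admission risk.

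**Formula.** Let p be the true admission risk, w the proportion withdrawn, and u the share of withdrawers' 12-month admission risk that no source sees. Under the zero rule:

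- observed risk = p × (1 − w × u)
- observed ratio = true ratio × (1 − w_PAAP × u) / (1 − w_UC × u)

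u = 1 means withdrawal at day 0 and no capture by HES, calls or earlier records. u = 0.5 corresponds to mid-year withdrawal with nothing captured afterwards. u = 0 means full capture.

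**Ratios under the zero rule.**

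| Withdrawal, usual care / PAAP | u | Factor | True 1.00 becomes | True 1.50 becomes |
|---|---|---|---|---|
| 10% / 10% | any | 1 | 1.00 | 1.50 |
| 5% / 15% | 1 | 0.85/0.95 | 0.89 | 1.34 |
| 5% / 15% | 0.5 | 0.925/0.975 | 0.95 | 1.42 |
| 15% / 5% | 1 | 0.95/0.85 | 1.12 | 1.68 |
| 15% / 5% | 0.5 | 0.975/0.925 | 1.05 | 1.58 |
| either | 0 | 1 | 1.00 | 1.50 |

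**Absolute scale.** Equal withdrawal does not protect absolute measures. With 10% in each arm and u = 1, a 5% risk is seen as 0.05 × 0.90 = 4.5%, and a true excess of 2.5 points as 2.5 × 0.90 = 2.25 points. A mean difference in hospital days, the measure in section 5.2, shrinks by the same factor.

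**Would copying the mortality rule be enough?** That rule sets withdrawers to missing only if no event was seen, so it keeps events and drops non-events. Take mid-year withdrawal of 5% / 15%, no later capture, a 5% true risk and no effect:

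- usual care: events 0.05 × 0.975 = 0.04875; missing 0.05 × 0.975 = 0.04875; risk 0.04875/0.95125 = 5.12%
- PAAP: events 0.05 × 0.925 = 0.04625; missing 0.15 × 0.975 = 0.14625; risk 0.04625/0.85375 = 5.42%
- ratio 5.42/5.12 = 1.06

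The bias changes direction, from 0.95 to 1.06. Removing every participant without coverage, whether or not an admission was seen, gives 5%/5% = 1.00 under the same assumptions.

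**The case against.** The strongest reply is that notes review is only one of three sources. An admission found in HES, at a day 28-30 call, or in records before withdrawal is still counted, so it does not follow that everyone who withdrew is scored as never admitted. This stands: the problem is confined to participants for whom all three sources are empty after withdrawal. A reader might infer from the mortality rule that HES stops at withdrawal. The SAP does not show that. The rule speaks of withdrawal from note review or follow-up, and the consent terms for linkage are not in the document. HES coverage is unknown, neither lost nor assured.

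Second, no withdrawal rate is given, and differential withdrawal is only plausible. The trial is open label with a clinic test in one arm, but section 2.4 says that PAAP participants who do not attend testing are still followed up unless they withdraw consent. With equal withdrawal the ratio is unbiased. This also stands, though it does not rescue the absolute measures.

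Third, a reader might extend the point to MRSA and *C. difficile* (sections 2.1.2.6 and 2.1.2.7), which also lack a missing-data rule. Those sections state no zero default, so nothing in them says that unobserved participants are coded negative. The point does not reach them.

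**Conclusion.** The point holds as an inconsistency in how declared safety outcomes are coded. Followed as written, section 2.1.2.4 turns unobserved follow-up into observed zeros, explicitly for the count and the days and by implication for the binary outcome. Comparable outcomes in the same SAP are set to missing.

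Its likely size is modest. With no true effect and an assumed 5% v 15% withdrawal, the ratio is about 0.95 if withdrawal is mid-year without HES capture. The 11% apparent reduction (0.89) is the extreme of that scenario, needing withdrawal at day 0 and no capture from any source, and should not be read as the expected effect. With full HES capture there is no bias on any scale; with equal withdrawal the ratio is 1.00 but absolute risks are still understated. The direction depends on which arm loses more participants. If PAAP does, a true excess of admissions is understated.

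The primary outcome and the sample size are unaffected. The change should still be made before analysis, because it concerns safety and costs little.

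**What to change.** In section 2.1.2.4:

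1. Code zero or 'no' only where notes review or HES linkage covered the 12-month period. For the 56-day outcomes, also require that the records identifying primary events were available. An admission in HES cannot be assigned to a primary event that nobody could see.
2. In the main analysis of these outcomes, treat participants without that coverage as missing on the basis of coverage, not on whether an admission was recorded. For the count, observed time as an offset is an alternative that keeps partial follow-up.
3. State how the coverage rule treats death before 12 months and the incomplete follow-up anticipated in section 6.3.
4. Apply the same rule to the exploratory 12-month versions in section 8, where HES alone may be sufficient coverage.
5. Report the number affected per arm, and show the zero-coded version as a sensitivity analysis.

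The cost is SAP wording and one extra analysis run; no new data are needed. The downside is that a few participants, including some with a recorded admission, leave the denominators. The result also still assumes that loss of coverage is unrelated to admission risk given the model covariates.
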